Baseline Visit 2 (RAAS Characterization): After Baseline Visit 1, subjects will be placed on an isocaloric low sodium diet for 6 days prepared by the metabolic phenotyping core at the BWH Center for Clinical Investigation for assessment of RAAS activation. Subjects will be asked only to consume the prescribed diet, containing 10 ± 2 mEq Na⁺, 100 ± 2 mEq K⁺, and 1000 ± 50 mg Ca²⁺ per 24 hours.

- 1) 24 hr urine will begin on the morning of this visit for volume, Na, K, Cr, cortisol, and aldosterone excretion rate.
- 2) Urine pregnancy test for females as appropriate.
- 3) Urine Na and Cr (rescheduled if subject is not in sodium balance).
- 4) Interval history and physical, including orthostatics.
- 5) Subjects will begin fast and lie supine overnight.
- 6) Fasting blood for PRA, serum aldosterone, K. DNA collection for genetic testing is optional.
- 7) Resume ad lib diet and administer study medication (eplerenone vs. placebo) to be started on the following day.

Substudy Visit 1 (Optional): Subjects will present on a low carbohydrate diet, after an overnight 12 hr fast. We will obtain:

- 1) STAT serum pregnancy test for females as appropriate.
- 2) Cardiac ¹⁸F-FDG-PET/CT to assess arterial inflammation.

Randomization and Blinding: Subjects will be randomized 1:1 to receive eplerenone

**Mineralocorticoid Receptor Antagonism for Cardiovascular Health in HIV
The MIRACLE HIV Study**

50mg daily or identical placebo for 12 months. The randomization list, stratified by gender, statin use and presence of plaque will be generated by the biostatistician and kept by the research pharmacy. Daily dosing starts at 50 mg daily for the first week to avoid hypotension and will be increased to 50 mg twice daily at the 1 week safety visit. The study will be double-blinded. All subjects will receive lifestyle modification as described below.

Safety Visits (1 wk, 2 wk, 4 wk, 3 mo, 6 mo, 9 mo post baseline visits): Subjects will only present after an overnight 12 hr fast for the 6 month visit. All safety visits include:

- 1) Urine pregnancy test for females.
- 2) Interval history and physical, including vitals.
- 3) Blood for Cr, K. Blood for markers of heart disease and inflammation for the 6 month visit only.
- 4) Collection of used study drug and provision of new supply.

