- 5) Standardized lifestyle counseling as per goals derived from the AACE and NCEP-ATP III guidelines and modeled after the Diabetes Prevention Program. At the 1 week visit, the study dose will be escalated to 50mg twice daily as tolerated based on blood pressure and labs.

12 Month Visit: Same as Baseline Visit 1

Substudy Visit 2 (Optional): Same as Substudy Visit 1

COVID19 Contingency Plan: MGH and BWH have instituted restricted visits for research purposes in response to the evolving COVID-19. These restrictions have prompted the following changes to the study:

1) We may conduct visits remotely until restrictions are lifted. Remote visits will be conducted over zoom video conferencing or telephone and every attempt will be made to keep the visit schedule the same. Changes may occur to the visit schedule due to factors related to covid19. During these visits, someone from the study staff will contact the subject (via zoom video conferencing or telephone) and may conduct the following research activities:

- Consenting*
- Obtaining information about past and present health
- Questionnaires
- Lifestyle Counseling
- Obtaining information related to safety assessments

2) We may ship study drug directly to the subject.

3) If blood work cannot be obtained at the study site, we may ask the subject to have labs performed locally. We will provide a lab requisition and help locate a facility.

4) We will try to arrange for assessments to occur remotely and continue to follow the visit schedule. Some study procedures require a visit to the study site, for example, imaging procedures. We may provide the subject with additional study drug until we are able to perform the study procedure, and this may extend the visit schedule. If a study procedure requires an in-person visit and cannot be scheduled at the study site due to

Mineralocorticoid Receptor Antagonism for Cardiovascular Health in HIV The MIRACLE HIV Study

COVID19 policies, then the procedure may be omitted.

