Eplerenone: The eplerenone dose of 50mg daily has been used safely in previous studies to improve coronary circulation in individuals with Type 2 diabetes and by others in numerous studies of patients with CVD. This dose is FDA approved for indefinite use in patients with hypertension or left-ventricular dysfunction following myocardial infarction. Hyperkalemia is a potential side effect of eplerenone use, and any subject with serum K > 5.5 mEq/L at screen will be excluded. During the study, a subject who has an elevated K of > 5.5 mEq/L at any study visit will have a recheck; if the K remains elevated after recheck, the dose will be decreased to 50mg daily. If the K remains elevated > 5.5 mEq/L, the subject will be excluded from the study. Additionally, subjects who experience symptoms of hyperkalemia and have a K > 5.0 mEq/L will be excluded from continued participation in the study. Subjects who have hypotension (SBP<90 mmHg) at any study visit after titration to full dose eplerenone 50mg twice daily will be given a dose reduction to 50 mg daily. If a subject remains hypotensive (SBP <90 mmHg) or symptomatic of hypotension at the reduced dose they will be dropped from the study. Since subjects with renal insufficiency may require reduced dosing based on creatinine clearance, subjects with serum creatinine > 1.5 mg/dl will also be excluded. Other rare side effects include dizziness, fatigue, and diarrhea; these will be assessed for throughout the study. The effect of eplerenone on an embryo, fetus, or on a breastfeeding infant, is unknown and may be harmful. Because of these unknown risks, women cannot take part in this study if they are: pregnant, trying to become pregnant, breastfeeding. If women become pregnant or think they are pregnant during the study, they must stop taking the study medication and will be withdrawn from the study. We have received FDA IND exemption for the use of eplerenone in HIV for insulin resistance and recently received an FDA IND exemption for application in CVD indices in HIV. Protease inhibitors with the most significant effect on CYP3A4 will be exclusionary as in our prior trials of HIV patients. We will also exclude subjects using other strong inhibitors of CYP3A4, as well as CYP3A4 inducers. Furthermore, all subjects will be carefully monitored for side effects, including frequent potassium and BP monitoring. A 50mg twice daily dose of eplerenone has been chosen, such that even if concentrations do increase somewhat through pharmacokinetic interactions, we expect the drug to be well tolerated. The dose of 100 mg/day has been effective in numerous studies of non-HIV patients and is expected to be effective in the proposed studies.

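### The COVID contingency does not require a K/Cr result at remote safety visits, names no remote route for BP or pregnancy testing, and sets no safety tests for dosing extended past month 12

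*Combined protocol and SAP*

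**What the plan says.** **Ordinary conduct.** Section V, Safety Visits, sets visits at weeks 1, 2 and 4 and months 3, 6 and 9. The list headed "All safety visits include" contains a urine pregnancy test for females, an interval history and physical with vitals, blood for Cr and K, and the exchange of used for new study drug. The week-1 increase to 50 mg twice daily depends on blood pressure and laboratory results. Potassium is measured again at the Bionutrition Visit before month 12 and at the 12 Month Visit.

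**Contingency.** The COVID19 Contingency Plan in the same section is introduced with "These restrictions have prompted the following changes to the study". Four provisions matter here:

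- Item 1 allows video or telephone visits. Its list of remote activities has one general entry on gathering safety information. BP and pregnancy testing are not named.
- Item 2: "We may ship study drug directly to the subject".
- Item 3: "If blood work cannot be obtained at the study site, we may ask the subject to have labs performed locally". Staff will supply a requisition and help to find a facility.
- Item 4 says staff will try to arrange remote assessments. For procedures that need the site, such as imaging, it allows "additional study drug until we are able to perform the study procedure, and this may extend the visit schedule". If such a procedure cannot be scheduled because of "COVID19 policies, then the procedure may be omitted".

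**Rules that use these measurements.** Section VII, Eplerenone, states that "a subject who has an elevated K of > 5.5 mEq/L at any study visit will have a recheck". It requires a dose reduction for SBP below 90 mmHg after titration to full dose, and it stops study drug in pregnancy. Section IX has a matching potassium rule, and drops a subject who stays below SBP 90 mmHg, or symptomatic, after a dose reduction.

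**The concern.** The contingency governs a subject seen remotely, and its wording is weaker than that of the safety-visit list it modifies. A fixed draw becomes something staff may request. Vitals and the pregnancy test have no stated remote counterpart. Dosing can be prolonged with no end date and no attached monitoring.

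The stake is patient safety. The target dose is 100 mg per day of a drug for which the protocol names hyperkalemia and hypotension as the risks to manage. The management rules act mainly on a measured potassium or a measured SBP. A telephone call can elicit symptoms, and it can elicit a suspected pregnancy. It cannot detect an asymptomatic high potassium, a rising creatinine or a low blood pressure. The entry criteria exclude only K above 5.5 mEq/L, so a subject may start at the action threshold itself.

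**Working it through.** The plan states no figure to reproduce. The check compares the texts and then subtracts calendar dates.

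**Texts side by side**

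| Measurement | Safety Visits (ordinary) | Contingency (remote) | Rule that needs it |
|---|---|---|---|
| K, Cr | every visit | staff may request a local draw; no result or window required | K > 5.5 mEq/L: recheck, then reduce dose or withdraw |
| BP | every visit, with vitals | no method named | SBP < 90 mmHg: reduce dose, then withdraw |
| Urine pregnancy test | every visit, females | no method named | stop drug and withdraw |
| Dosing past month 12 | not foreseen | allowed, no maximum, no tests named | all of the above |

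**Longest gap between potassium values**

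Inputs: K at weeks 1, 2 and 4 and months 3, 6 and 9 (Safety Visits), at the Bionutrition Visit before month 12, and at month 12. One week = 12/52 = 0.231 months, so week 2 = 0.46 and week 4 = 0.92 months.

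Assumption A: the end-of-study Bionutrition K falls 4 to 1 weeks before month 12, at month 12 − 0.92 = 11.08 to month 12 − 0.23 = 11.77. The documents give no interval.

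Assumption B: under an extension, the Bionutrition Visit, which carries the on-site coronary CTA, moves with the 12 Month Visit, and no local K is drawn meanwhile. The length of deferral is also assumed.

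| Case | Subtraction | Longest gap (months) |
|---|---|---|
| As scheduled | 6 − 3 or 9 − 6 | 3.0 |
| No K at month 3 | 6 − 0.92 | 5.1 |
| No K at month 6 | 9 − 3 | 6.0 |
| No K at month 9 (A, 4 weeks) | 11.08 − 6 | 5.1 |
| No K at month 9 (A, 1 week) | 11.77 − 6 | 5.8 |
| End-of-study visits deferred 1, 2 or 3 months (B), no earlier K missed | 13 − 9, 14 − 9, 15 − 9 | 4, 5 or 6 |

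A single missed early draw does not lengthen the longest gap. Without the week-4 K, for example, the interval is 3 − 0.46 = 2.5 months. The exposure lies in the quarterly visits and in any extension.

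Each figure holds only if no other test is done in the interval.

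**The case against.** The strongest reply is that item 3 changes where blood is drawn, not whether. The safety-visit list is never withdrawn, the requisition is promised in firm language, and the whole contingency is drafted permissively. Sections VII and IX still promise frequent potassium and BP monitoring and serial checks of kidney function. This reading is fair, so the documents do not support saying that the contingency cancels the K/Cr requirement. What remains is that no sentence requires a result at a remote visit, and the general promises give neither an interval nor a remote method.

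Three further inferences are tempting and should not be drawn:

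- **That the contingency removed a check on drug supply.** In ordinary conduct new drug is handed out at the same visit as the blood draw, and no sentence makes it wait for the result. Only the week-1 escalation depends on laboratory results, and the contingency does not waive that. The missing supply condition is common to both settings.
- **That the omission clause lets staff drop potassium tests.** It covers procedures that need the site, with imaging as the example, and item 3 gives blood work an off-site route. The clause fits K/Cr poorly. It simply does not say that safety measurements fall outside it.
- **That subjects went unmonitored.** No missed test is documented, and a local draw under item 3 could close any extension gap.

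Other mitigation is real. Exclusion of ACE inhibitors, ARBs, potassium supplements, eGFR below 60 and strong CYP3A4 inhibitors lowers the risk. A physician is on call at all hours, creatinine is checked before each MRI, and the data safety monitoring board reviews adverse events quarterly. None of these supplies a potassium or BP value between visits.

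**Conclusion.** The point stands as a gap in required safety measurements under the contingency. Followed as written, it allows a subject to continue on up to 100 mg per day of eplerenone without the potassium and SBP values on which the protocol's own rules act.

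One missed quarterly potassium moves the longest gap from 3 months to about 5 to 6 months. The month-9 case rests on assumption A. The 4 to 6 months under an extension is illustrative only, because it rests on assumption B and an assumed deferral of 1 to 3 months. The documents do not give the number of subjects seen remotely or extended, or the chance that an abnormal value would be missed, so no expected harm can be computed. The case for acting is that the rules already exist, the intervals already exist, and only the link to remote conduct is missing.

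**What to change.** **Item 3.** Change 'may ask' to 'will ask'. State that K/Cr remains required at each remote safety visit, drawn locally if the site is unavailable. Add BP by home cuff or at a local site, and a home urine pregnancy test for females.

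**Item 4.** State that if dosing runs past month 12, K/Cr, BP and (females) a pregnancy test are obtained at least every 3 months, the spacing already used at months 3, 6 and 9. State that the omission clause does not apply to these safety tests.

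The potassium and SBP thresholds, the endpoints and the analysis do not change.

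**Optional.** Shipment or extra supply could be made to depend on a recent K/Cr, for example within 14 days, with a short bridging supply while a result is pending. This is stricter than the on-site rules and could interrupt treatment during restrictions, so the amendment does not need it.

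**Cost.** A short amendment, home cuffs and urine kits for subjects seen remotely, and a local blood draw at a time when facility visits are themselves a burden.

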***COVID19 Contingency Plan for Informed Consent:**

A consent form may be mailed or emailed to the subject and a licensed physician or nurse practitioner will arrange a phone call or zoom video conference with the subject to review the consent form in detail. The consent form will be signed and completed via one of the following options: 1) If the subject has electronic capabilities/internet to use REDCap, the consent form will be electronically signed by both parties and a PDF of the consent form will be available for both the subject and the licensed physician or nurse practitioner, or 2) The subject will sign the consent form during the phone discussion and either mail/email the signed form to study staff or bring the signed form to the next in person visit at which time the consent form will be signed by the licensed physician or nurse practitioner, or 3) To minimize exposure time between the subject and study team, an iPad may be offered to the subject to perform a zoom video conference with the licensed physician or nurse practitioner to discuss the consent form prior to meeting in the same room to sign the consent form. Study procedures will not be performed prior to obtaining informed consent and obtaining a copy of the signed consent form.

Study Procedures

Computed Tomography (CT) Abdomen

Images will be acquired via single-slice acquisition through L4 with tube current of mA, voltage of 80kV and 70mAs, slice thickness 10 mm, and 45 cm field-of-view.

Coronary Computed Tomography Angiography (CTA)

Contrast-enhanced CCTA allows for non-invasive assessment of atherosclerotic plaque burden and morphology. Image acquisition will take place at MGH using the SOMATOM Definition Flash, a dual source 128 detector row CT scanner, or the SOMATOM Force, a dual source 196 detector-row CT scanner (Siemens Healthineers, Forchheim, Germany). Semiautomated reference tube current selection and exposure control (CAREDose 4D) are tailored to the subject's body size, in conjunction with semiautomated reference tube potential (voltage) selection (CARE KV), with individually adapted exposure settings on a per-patient basis. Prospective ECG-triggered axial-sequential or retrospective ECG-gated spiral with adaptive pulsing scan modes are used based on the heart rate and rhythm. Iterative image reconstruction algorithms allow for further reductions in radiation dose.

The CCTA protocol is as follows, and is based on the standard clinical CCTA protocol at MGH: Prior to imaging, intravenous (IV) access will have been obtained in an arm or hand vein, usually in the right antecubital vein. The subject's blood pressure will be taken, and ECG leads will be attached to monitor heart rate and rhythm. Sublingual nitroglycerin (0.3-0.9 mg, typically 0.6 mg) or transdermal nitroglycerin (0.6-0.8 mg/hr for ~45 minutes) will also be administered as per standard protocol for cardiac CT scans. Contraindications to nitroglycerin include known narrow angle glaucoma, hypotension with systolic blood pressure < 90 mm Hg, known severe aortic stenosis, or use of phosphodiesterase type 5 inhibitor (e.g. sildenafil, tadalafil, vardenafil) within the 5 days prior to scan. A prospectively-ECG triggered noncontrast CT of the heart is obtained to measure coronary calcium. The test bolus method will be used to plan the CTA timing, via a test bolus injection of nonionic iodinated contrast medium (approximately 20 ml), followed by a flush of saline solution (approximately 40 ml). Contrast-enhanced CT

Mineralocorticoid Receptor Antagonism for Cardiovascular Health in HIV The MIRACLE HIV Study

acquisition will then take place. Based on subject size, 60-100 ml of nonionic iodinated contrast (iopamidol 370 g/cm³, Isovue 370, Bracco Diagnostics, Princeton, NJ) will be injected, followed by a flush of 40 ml of saline solution. After a delay based on the test bolus, a CT acquisition will be performed from the aortic arch to the diaphragm: tube voltage 70 - 120 kVp, tube current-time product reference 320 mAs, detector collimation 2 x 128 x 0.6 mm or 2 x 196 x 0.6 mm. A number of high-resolution images of the heart at slightly different time-positions within the cardiac cycle will be reconstructed, of which the best phase will be used to evaluate the coronary artery lumen, plaque distribution, and plaque morphology.

Cardiac Positron Emission Tomography (PET)

Regional and global coronary blood flow will be assessed using PET imaging. Vasoactive medications and beta-blockers will be withheld on the morning of the study. Subjects will be allowed to continue using nitroglycerin as needed. Studies will be performed after at least 4 hours of fasting. The protocol will take approximately 2.5 hours, including patient preparation. Regional coronary blood flow will be measured at rest and during an intravenous (IV) infusion of regadenoson (0.4mg) or adenosine (0.14 mg/kg/min) using ¹³N-ammonia as a flow tracer. After IV administration of ¹³N-ammonia (20 mCi), serial images will be acquired for 20 min, as previously described. After 30 min, IV regadenoson or adenosine will be infused for 4 minutes. Two minutes into the regadenoson or adenosine infusion, a second dose of ¹³N-ammonia (20mCi) will be injected and images recorded again in the same sequence. HR, BP, and 12-lead ECG will be recorded at baseline and every minute during and after the infusion of regadenoson or adenosine. All images will be analyzed by an expert in cardiac PET blinded to treatment assignment.

Cardiac Magnetic Resonance Imaging (MRI)

T1 imaging before and after contrast, using a breath-hold, modified Look- Locker imaging (MOLLI) technique, will be used for mapping of the total and segmental extracellular volume fraction to detect expansion of the extracellular matrix. Typical MOLLI acquisition parameters are: TR/TE=2.14/1.07 ms, flip angle=35°, FOV= 340x255mm, matrix=192x144, 107 phase encoding steps, interpolated voxel size= 0.9x0.9x8mm, parallel acceleration factor=2 with 24 reference lines (iPAD), cardiac trigger delay TD=500ms; 206 ms acquisition time per SSFP image read-out. The pre-contrast T1 mapping will use a 5(2)-3 MOLLI scheme, while the post-contrast T1 measurements will use a 4(2)-3(2)-3(2) scheme, where the numbers in brackets indicate the duration of the rest period as a multiple of the R-to-R duration. The post-contrast T1 measurements are interleaved with the other MR protocol components, such that T1 measurements are not performed within less than 5 minutes of a contrast injection to assure contrast-equilibrium between tissue and blood. Multiple T1 measurements are used with regression analysis to obtain an accurate estimate of extracellular volume (ECV) fraction, thereby improving upon the precision of “two-point” measurement protocols.⁶⁶ Only R1 data-pairs with R1 in blood < 3.5 s-1 will be used to meet the conditions of fast transcytolemmal water exchange, underpinning the linear model for ECV.⁶⁷ ECV will be multiplied by LV mass index and reported as ECVi (g/m²). The T1 protocol comprises one pre-contrast measurement, and 3 post contrast measurements as outlined above. Microvascular coronary function via a combination rest/stress MRI perfusion study will be quantified. Study subjects will be administered regadenoson (5 ml containing 0.4 mg regadenoson bolus via IV, followed by flush) or adenosine (400 microgram bolus via IV, followed by flush). A saturation-recovery prepared fast

MIneralocorticoid Receptor Antagonism for CardiovascuLar hEalth in HIV The MIRACLE HIV Study

“TurboFLASH” gradient echo-technique, with iPAT (with mSENSE) acceleration (x2) will be used to measure perfusion at rest and after vasodilatory stress in three slices (basal, mid, apical levels) with an in-plane resolution of 2.2 x 2.2 mm in three short-axis slices, using TR/TE/flip = 2.3/1.0/18°; 10 msec delay after saturation before image read-out; linear phase-encoding order. In addition, a low-resolution TurboFLASH image is acquired within 50 ms during each heart-beat at the basal level. This low resolution image has a T1-weighting that allows to measure the arterial input function (AIF) without significant signal saturation⁶⁸. (Siemens software patch WIP578 for syngo MR B17). The saturation-recovery time for the AIF readout is kept to < 20 ms. The software also automatically generates motion-corrected images (in addition to the “raw” images), which substantially reduces the post-processing time for quantification of myocardial perfusion (reserve). A contrast bolus dosage of 0.06 mmol of Dotarem (gadoterate meglumine, Guerbet, Inc.) is injected to allow coronary blood flow quantification using the arterial input measured with the low-resolution AIF “scout”, and keeping arterial *and* myocardial signal saturation to < 5%. (We use a dosage of 0.06 mmol/kg for this reason, rather than 0.1 mmol/kg used by Gatehouse et al⁶⁸, though this dosage is fully adequate for analyzing myocardial contrast enhancement.). Rest perfusion imaging will be performed > 20 minutes after stress perfusion imaging. We will quantify coronary blood flow, as we have done previously.^{69,70} The rationale for acquiring perfusion images with MRI in parallel with the PET studies, is the higher spatial resolution of MRI compared to PET to assess myocardial blood flow in the endocardial layer, and also determine the ratio of endo- to epi-cardial flows, as a marker of ischemia. For post-processing, the perfusion images will be segmented along the endo- and epi-cardial borders of the LV, and a reference point will be placed at the anterior LV/RV junction. Coronary blood flow will be quantified by model-independent deconvolution of the myocardial signal curves with the AIF. Myocardial signal curves for endo- and epicardial layers in 16 segments of the AHA segmentation model will be analyzed. All images will be analyzed by an expert in cardiac MRI blinded to treatment assignment.

Abdominal MRI

Images will be acquired using an axial T1-weighted fat suppressed pulse sequence obtained at the level of L4 vertebral body. Abdominal visceral and subcutaneous fat areas from MRI and CT are determined based on offline analysis of tracings obtained utilizing commercial software (Vitrak, Merge e/Film).

Nutritional Analysis and Dietary Protocol

Protein, carbohydrate, fat, micronutrient, dietary supplements and alcohol intake will be determined from 4-day food records (Nutrition Data systems). For 6 days prior to Baseline Visit 2 (RAAS characterization), subjects will be provided low sodium meals and snacks (10 mEq daily sodium, 100 mEq potassium, 1000 mg calcium, water intake ad lib) and they will be asked not to consume any food not provided to them, including no caffeine or alcohol. For 3 days prior to Baseline Visit 1 and 12 Month Visit, subjects will be provided sodium supplements through broth packets as needed to achieve urinary Na >200mmol/24 hr, and they will be asked not to consume any food not provided to them, including no caffeine or alcohol. Urine aliquots for sodium and creatinine and 24hr urine sodium will be measured for the period immediately prior to each visit to ensure compliance with the diet.

Lifestyle Modification

Goals derived from the AACE and NCEP-ATP III guidelines and the Diabetes Prevention Program are as follows: ≤35% calories from fat, < 7% calories from saturated fat, up to

Mineralocorticoid Receptor Antagonism for Cardiovascular Health in HIV The MIRACLE HIV Study

10% calories from polyunsaturated fat, reduction of trans fatty acid intake, up to 20% calories from monounsaturated fat, and 25-35g of fiber per day. 3 hrs of physical activity/week at moderate intensity. The curriculum is modeled after the Diabetes Prevention Program. Subjects will complete lifestyle sessions at the Clinical Research Center at MGH with nutritionists trained to implement the curriculum. The curriculum will be introduced and reinforced until the completion of the study.

Optional Substudy:

Cardiac 2-deoxy-2-18F-Fluorodeoxyglucose Positron Emission Tomography/ Computed Tomography (¹⁸F-FDG-PET/CT)

An approach to detecting macrophage activity in atherosclerotic plaques uses FDG as the contrast radiotracer for positron emission tomography (PET). FDG competes with glucose for uptake into metabolically active cells, including macrophages in atherosclerotic plaques, and is trapped inside cells after phosphorylation. FDG-PET can image metabolic activity (as a marker of plaque inflammation) quantitatively in atherosclerotic plaques^{71,72}, has been shown to have high reproducibility⁷³, and correlates with histologic data⁷². Taking advantage of the myocardium's preference for free fatty acids over glucose as an energy source, to minimize myocardial glucose uptake in order to better visualize coronary plaque activity, patients will be asked to adhere to an Atkins style diet for the evening prior to imaging and then to fast overnight. A fasting glucose will be checked prior to the start of the study. Cardiac PET/CT imaging will be performed two hours following intravenous administration of approximately 10mCi of ¹⁸F-FDG. Imaging will be performed using a Siemens Biograph PET/CT system (Siemens Medical Solutions, Forchheim, Germany). Semi automated co-registration of PET and CT images will be accomplished using the Siemens MultiModality WorkPlace TrueD (Forchheim, Germany). Once co-registered, the standardized uptake value (SUV) of FDG will be measured in various arteries. The SUV is the decay-corrected tissue concentration of FDG (in kBq/ml) divided by the injected dose per body weight (kBq/g). Target-to-background ratio (TBR) will be calculated for each vascular segment as the segment SUV divided by vena cava or atrial blood SUV. All images will be analyzed by an expert in cardiac FDG-PET/CT blinded to treatment assignment.

VI. Biostatistical Analysis

Statistical Consideration: Aim I: The primary endpoint is change in CFR assessed by cardiac PET or change in sMBF by cardiac MRI. Secondary endpoints will include the following: change in sICAM and sVCAM. Shapiro-Wilk test will be used to assess for normality of distribution, and variables that are not normally distributed will be appropriately transformed prior to inclusion in multivariable models. We will compare the change in CFR from months 0 to 12 between treatment groups (eplerenone vs. placebo) using student's t-test for variables that are normally distributed or Wilcoxon rank sum test for variables that are not normally distributed. We will also compare changes in sICAM and sVCAM over 12 months between treatment groups using similar statistical methods. In all Aims, for subjects who withdraw after 6 months, but before the final 12 month visit, we will obtain biomarkers and imaging similar to that scheduled for the final 12 month visit if the subject agrees to have end of study testing. The analysis will be intention to treat (ITT). In order to properly handle subjects with missing outcomes (those who withdrew before 12 months), we will apply longitudinal linear mixed effects model analysis with random subject level intercepts and time slopes by which the longitudinal treatment effect can be examined by testing the significance of

Mineralocorticoid Receptor Antagonism for Cardiovascular Health in HIV The MIRACLE HIV Study

time x treatment interaction, which will provide unbiased effect estimate under missing at random condition, which will be carried out by using augmented data sets created by multiple imputation. A sensitivity analysis will be performed to include only those subjects who completed the study. Baseline variables will be compared between treatment groups, and any variable that is statistically different between groups will be controlled for using multivariable modeling. It may be that subjects with more significant RAAS activation and dysregulation in aldosterone at baseline) are more responsive to eplerenone. We will phenotype the RAAS in subjects at the low sodium visit and, guided by this data, may use aldosterone levels prior to intervention as an index of RAAS activation and a covariate in assessing treatment response, to determine if eplerenone is more effective in the subpopulation with greater baseline aldosterone dysregulation and RAAS activation. Covariates that will be considered for inclusion in modeling, include variables that differ at baseline and those variables that may affect vascular dysfunction, inflammation, fibrosis and plaque (age, race, gender, BP, tobacco/illicit drug use, family history of CVD, lipids, and glucose), HIV parameters (viral load, CD4, and duration of HIV and ART use) and compliance. This will permit us to assess relevant factors that may mediate the effect of eplerenone on CFR in HIV and interactions between HIV and traditional risk factors contributing to eplerenone effects. Moreover, we will compare changes in CFR and vascular biomarkers over 12 months using regression analysis. We will perform Pearson's correlation for variables that are normally distributed and Spearman's correlation for variables that are non-normally distributed. If we see significant changes in specific biomarkers that correlate with changes in CFR, then we will run those specific biomarkers from stored serum at earlier time points (e.g. 6 months) to see if early changes in biomarkers can predict changes in CFR, as well as predict response to MR blockade. **Biostatistician Role:** The biostatistician will monitor data collection, quality and completeness of the study throughout all years of the grant. The biostatistician will create the randomization plan, using a permuted block algorithm, stratified for gender, statin use, and presence of plaque and provide the list to the study pharmacist (investigators will remain blinded). Identical placebo will be provided by the pharmacy. **Sample Size Determination:** Preliminary data from HIV subjects presented in this grant demonstrate a CFR 1.74 ± 0.73 (mean \pm SD) using cardiac PET. Supportive data are also derived from a longitudinal study by our team using cardiac PET, showing mean \pm SD change of CFR in diabetics treated with spironolactone 0.33 ± 0.83 vs. placebo: 0.02 ± 1.03 over 6 months (mean SD=0.93).⁴⁰ Given these data, we considered the range 0.73 - 0.93 SD to accurately reflect the potential variability of change in CFR for the proposed study. Based on this data, we now provide a range of detectable differences using 85% power and a revised increased sample size of 80 subjects, with an attrition rate of 15%, leaving 68 evaluable subjects. Thus, even choosing a conservative SD of 0.93, the study will be well powered to detect a difference in mean change of CFR of at least 0.69. As our preliminary data, using PET, show that HIV patients have a mean CFR 1.7, an increase of CFR to 2.4 with eplerenone is a clinically relevant increase associated with decreased morbidity and mortality. For the sMBF and biomarkers, this study has 85% power at a two-sided 0.05 α level to show a change in the variable of at least 0.74 SD after treatment with eplerenone vs. placebo.

Aim II: For this aim, the endpoint is change in myocardial ECV assessed by myocardial T1 mapping on cardiac MRI. Secondary endpoints will include the following: change in plasma IL-6, MCP-1, sCD163, sCD14 and serum hsCRP, galectin-3, cardiotrophin 1, lipocalin, PINP, PIIINP, BNP. Statistical algorithms as detailed in Aim I will be applied to

Mineralocorticoid Receptor Antagonism for Cardiovascular Health in HIV The MIRACLE HIV Study

these specific endpoints. Similar to Aim I, changes in ECV and inflammatory/fibrosis biomarkers over 12 mos comparing eplerenone vs. placebo will be assessed using ITT and longitudinal linear effects modeling with imputation and sensitivity analyses. By regression techniques and covariate analyses, we will also assess whether improvements in ECV from MR blockade will relate to improvements in diastolic strain.

Sample Size Determination: Thiara et al. show mean \pm SD ECV 0.28 ± 0.04 vs. 0.26 ± 0.03 in HIV vs. non-HIV using cardiac MRI.³⁰ To estimate the SD of change in ECV, we assumed an intrasubject longitudinal correlation over time $r=0.7$ among the HIV group, which results in a conservative SD estimate of 0.03. Based on this SD, the proposed study, with a revised sample size of 80 subjects and therefore 68 evaluable subjects considering a 15% attrition rate, will attain 85% power at a two sided α of 0.05 to detect a difference of at least 0.02 in longitudinal means of ECV. Thus our study is well powered to find a significant difference between arms that is clinically relevant, as each 0.03 increase in ECV raises the risk for mortality or CV morbidity by 50%.²³ For biomarkers, we have 85% power at a two-sided 0.05 α level to show a change of at least 0.74 SD comparing eplerenone vs. placebo.

Aim III: For this aim, the endpoint is change in noncalcified plaque volume assessed by coronary CTA. Secondary endpoints will include: change in high risk plaque morphology (numbers of low attenuation and positively remodeled plaque) by coronary CTA.

Statistical algorithms as detailed in Aim I will be applied to these specific endpoints. Moreover, the relationship between baseline CFR and non-calcified plaque volume will be assessed. Lastly, we will also determine whether longitudinal changes in coronary plaque are associated with changes in biomarkers of inflammation and immune activation to understand the potential relationship of these inflammatory indices as markers of improved indices of the coronary vasculature in response to MR blockade in the HIV. **Sample Size Determination:** In our prior studies assessing plaque in HIV, the median [IQR] change of noncalcified plaque volume over 12 mos was $6.7[-6.5, 29.8]$ mm 3 .¹³ We assumed a conservative SD of 18mm 3 taking the mean of the IQR. This study enrolling 80 subjects with 68 evaluable subjects will attain 85% power at a two sided α of 0.05 to detect a difference in noncalcified plaque volume of 13.3mm 3 between eplerenone vs. placebo, a clinically relevant change. For biomarkers, this study has 85% power at a two-sided 0.05 α level to show a change of at least 0.74 SD after treatment with eplerenone vs. placebo.

Aim IV: For this aim, the endpoint is change in MCP-1 between the low sodium and liberal sodium diets. Secondary endpoints will include: change in hsCRP, pentraxin3, IL6, Lp-PLA $_2$, sCD14, sCD163. We will test the change in biomarkers between the RAAS activated (sodium restricted) and RAAS suppressed states (sodium loaded) using the paired Student's t-test for normally distributed variables or Wilcoxon signed-rank test for non-normally distributed variables. We will apply Pearson's correlation for variables that are normally distributed and Spearman's correlation for variables that are non-normally distributed to determine whether there is a significant correlation between aldosterone during the RAAS activated state and TBR. Covariates considered for inclusion in modeling include variables that may affect vascular dysfunction, inflammation, and plaque (age, race, sex, BP, tobacco/illicit drug use, family history of CVD, lipids, glucose), and HIV parameters (viral load, CD4, duration of HIV and ART use). This will permit us to assess relevant factors that may mediate the effect of aldosterone on inflammation in HIV and interactions between HIV and traditional risk factors contributing to inflammation. **Sample Size Determination:** Preliminary data in HIV presented in this

